1. Visit 1 of this LT extension study should preferably be performed in one visit combined with the last visit of the preceding trial 1311.6 or during the interim period of maximum 5 days after completion of the last visit in 1311.6. If an EoT colonoscopy has not been performed during E1 within 1311.6, it must be performed between V1 and V2 in 1311.20/M15-989.
2. Assessments performed at the last visit in the previous trial do not have to be repeated at visit 1 in this trial. Assessments scheduled but not performed at the last visit in the previous trial should be repeated at Visit 1 in this trial, and the results entered into the CRFs of both trials 1311.6 and 1311.20/M15-989.
3. For patients who discontinue study medication before scheduled EoT visit, an early EoT visit should be performed. After last dose of study medication, a 140 day follow-up call should be scheduled. Upon EC/CA approvals of Study M16-000 protocol amendment 4, patients receiving treatment in M15-989 will have the option to enroll into M16-000 Sub-Study 3 after completing the EoT visit.
4. Must be performed at Visit 1 and starting from Visit 2 prior to each study drug administration in females of childbearing potential. In case of positive result, serum pregnancy test will be performed. Study drug will only be administered if pregnancy is ruled out.
5. Positive QuantiFERON-TB Gold In-Tube tests need not to be repeated. If TB or infection is suspected at any time during the study, a routine work up including chest x-ray and a QuantiFERON-TB Gold In-Tube test or an infection assessment must be performed at investigator's discretion and according to local guidelines.
6. Assessment of AE after subcutaneous injections will also include assessment of local tolerability. The assessment of local tolerability should be done just before the patient leaves the investigator site.
7. All assessments are to be completed prior to study drug administration, unless otherwise specified.
8. An end of trial call should be performed for both patients that agree to enroll into M16-000 Sub-Study 3 OLE or those that do not choose to participate.
9. For details of laboratory tests see [Section 5.2.3](#), [Table 5.2.3:1](#) and [Table 5.2.3:2](#).

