10. Every effort should be made for the patient to perform a final ileocolonoscopy at the study visit where the last dose of study medication is administered. For patients with early EoT, every effort should be made to perform a final ileocolonoscopy within 2 weeks following the early EoT visit.
11. Colonoscopy is not to be repeated if done at preceding visit.
12. IBDQ should be completed before site staff interaction and study drug administration.
13. Blood samples for PK and ADA will be drawn BEFORE drug administration, i.e. pre-dose, whenever visits coincide.
14. Visit 1.1 is applicable only for those patients that had visit E1 more than 5 days before Visit 1. Visit 1.1 can be performed by phone, fax or email.
15. IRT has to be called only once at V1 or V1.1 after assessment if s.c or i.v. re-induction is needed.
16. In case patient had visit E1 less than 5 days before Visit 1, CDAI assessment and new patient diary dispense should be done at Visit 1.

**FLOW CHART 2: PATIENTS (1) ROLLING-OVER AT WEEK 52 FROM PRECEDING TRIAL 1311.6
(WITH CLINICAL RESPONSE OR REMISSION AT VISIT E5) VISITS 1-18**

Trial Period	Screening														Treatment period						
	1 ^{1,2}	1.1 ^{1,4}	2	3	4	5	6	7	8	9	10	11	12	13	14	15	16	17	18		
Visit	0	1	6	14	22	30	38	46	54	62	70	78	86	94	102	110	118	126	134		
Week	+5	+5	±7	±7	±7	±7	±7	±7	±7	±7	±7	±7	±7	±7	±7	±7	±7	±7	±7		
Time window (days)																					
Informed consent	X																				
Assessment of eligibility	X																				
LABS/SAFETY ASSESSMENTS																					
Detailed physical examination	X																				
Targeted physical examination (incl. vital signs)		X	X	X	X	X	X	X	X	X	X	X	X	X	X	X	X	X	X	X	
Weight	X	X	X	X	X	X	X	X	X	X	X	X	X	X	X	X	X	X	X	X	
12 Lead Resting-ECG	X																				
Urine Pregnancy test ⁴	X		X	X	X	X	X	X	X	X	X	X	X	X	X	X	X	X	X	X	
Laboratory tests (serum chemistry, hematology, urinalysis) ⁹	X		X	X	X	X	X	X	X	X	X	X	X	X	X	X	X	X	X	X	
QuantiFERON-TB Gold In-Tube test ⁵	X																				

Trial Period	Screening							Treatment period											
	1 ^{1,2}	1,1 ¹⁴	2	3	4	5	6	7	8	9	10	11	12	13	14	15	16	17	18
Visit	0	1	6	14	22	30	38	46	54	62	70	78	86	94	102	110	118	126	134
Week																			
Time window (days)	+5	+5	±7	±7	±7	±7	±7	±7	±7	±7	±7	±7	±7	±7	±7	±7	±7	±7	±7
EFFICACY																			
ASSESSMENTS																			
Dispense patient diary for screening ¹⁴	X																		
Crohn's Disease Activity Index (CDAI), PRO-2	X ¹⁵	X	X	X	X	X	X	X	X	X	X	X	X	X	X	X	X	X	X

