Administration of trial s.c. medication ⁷	X	X	X	X	X	X	X	X	X	X	X

1. If an EoT colonoscopy has not been performed during E1/E5 within 1311.6, or if the patient had a treatment interruption followed by a clinical relapse, it must be performed between V1 and V2 in 1311.20/M15-989.
2. Assessments performed at visit E1/E5 in the previous trial do not have to be repeated at Visit 1 in this trial. Assessments scheduled but not performed at Visit E1/E5 in the previous trial should be repeated at visit 1 in this trial, and the results entered into the CRFs of both trials, 1311.6 and 1311.20/M15-989.
3. For patients who discontinue study medication before scheduled EoT visit, an early EoT visit should be performed. After last dose of study medication, a 140 day follow-up call should be scheduled. Upon EC/CA approvals of Study M16-000 protocol amendment 4, patients receiving treatment in M15-989 will have the option to enroll into M16-000 Sub-Study 3 after completing the EoT visit.
4. Must be performed at Visit 1 and starting from Visit 2 prior to each study drug administration in females of childbearing potential. In case of positive result, serum pregnancy test will be performed. Study drug will only be administered if pregnancy is ruled out.
5. Positive QuantiFERON-TB Gold In-Tube tests need not to be repeated. If TB or infection is suspected at any time during the study, a routine work up including chest x-ray and a QuantiFERON-TB Gold In-Tube test or an infection assessment must be performed at investigator's discretion and according to local guidelines.
6. Assessment of AE after intravenous infusions and subcutaneous injections will also include assessment of local tolerability. The assessment of local tolerability should be done just before the patient leaves the investigator site.
7. All assessments are to be completed prior to study drug administration, unless otherwise specified.
8. An end of trial call should be performed for both patients that agree to enroll into M16-000 Sub-Study 3 OLE or those that do not choose to participate.
9. For details of laboratory tests see [Section 5.2.3](#), [Table 5.2.3.1](#) and [Table 5.2.3.2](#).
10. Every effort should be made for the patient to perform a final ileocolonoscopy at the study visit where the last dose of study medication is administered. For patients with early EoT, every effort should be made to perform a final ileocolonoscopy within 2 weeks following the early EoT visit.

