3. DESCRIPTION OF DESIGN AND TRIAL POPULATION

3.1 OVERALL TRIAL DESIGN AND PLAN

This open label long term extension trial investigates the long term safety and efficacy of BI 655066/ABBV-066 (risankizumab). Approximately 60 patients who meet the entry criteria are planned for inclusion in this trial, rolling over from preceding trial 1311.6. The treatment will be open label.

The treatment period will be 204 ([Flow chart 1](#)), 206 ([Flow chart 2](#)) or 216 ([Flow chart 3](#)) weeks, followed by a 140 day follow up period.

Patients rolling over from preceding trial 1311.6 will have to complete period 2 or 3 in that trial and either demonstrate a clinical response without remission at Visit E1 or a clinical response or remission at Visit E5 as defined by that protocol (see Figure 3.1:1).

[figure not shown]

Figure 3.1:1 Guideline for roll over of patients from 1311.6 to long term extension study 1311.20/M15-989

All patients directly rolled over from 1311.6 into 1311.20/M15-989 will receive 180 mg BI 655066/ABBV-066 (risankizumab) subcutaneously from visit 2 onwards every

8 weeks, until the EoT visit is performed. Patients who complete this study may elect to continue in M16-000 Sub-Study 3 (Phase 3 open label extension study).

Patients who have completed 1311.6 qualifying for roll-over into 1311.20/M15-989 before availability of this study, can be enrolled depending on their clinical remission or response. If patients were treated between finishing 1311.6 and entering 1311.20/M15-989 with anti-TNF therapy or any biologic agent an 8 weeks or 5 times the half-life (whichever is longer), wash-out period will be needed before administration of first i.v or s.c. study medication. Patients must maintain their best response status (clinical response or remission) post 1311.6. Patients who dropped from 1311.6 with remission must maintain remission or undergo re-induction while responders will have to maintain their response.

- If clinical response or remission (CDAI drop >100 from baseline of 1311.6 or CDAI < 150) was maintained after end of treatment and is confirmed at screening for 1311.20/M15-989, patients can directly be assigned to open label s.c. maintenance treatment with 180 mg every 8 weeks (FLOW CHART 1) (visit window between last IMP dose in 1311.6 and first IMP dose in 1311.20/M15-989 should be at least 8 weeks).

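### Footnote 2 of all three flow charts waives Visit 1 assessments with no maximum age, so a patient returning after a gap could be re-dosed on an old TB result, contrary to Protocol Section 2.3

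*Protocol*

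**What the plan says.** Footnote 2 is attached to the Visit 1 column of each flow chart and has two halves.

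- **No repeat.** Flow Chart 3: "Assessments performed at visit E1/E5 in the previous trial do not have to be repeated at Visit 1 in this trial". Flow Charts 1 and 2: "Assessments performed at the last visit in the previous trial do not have to be repeated at visit 1 in this trial".
- **Double entry.** Items scheduled at the end of 1311.6 but missed there are to be done at Visit 1, "and the results entered into the CRFs of both trials, 1311.6 and 1311.20/M15-989" (Flow Chart 3; the other two charts have the same rule).

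On timing, footnote 1 of Flow Charts 1 and 2 says that Visit 1 should preferably be combined with the last 1311.6 visit, "or during the interim period of maximum 5 days after completion of the last visit in 1311.6". Longer gaps are foreseen. Flow Chart 1, footnote 14: "Visit 1.1 is applicable only for those patients that had visit E1 more than 5 days before Visit 1". Flow Chart 2, footnote 14, says the same for E5. Flow Chart 3 has no 5-day sentence at all.

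Section 3.1 admits patients who completed 1311.6 before this study was available. For those who kept their response it gives a minimum only: "visit window between last IMP dose in 1311.6 and first IMP dose in 1311.20/M15-989 should be at least 8 weeks". It also provides a wash-out for patients given an anti-TNF agent or another biologic in between, although Section 4.1.2 describes early completers as not treated otherwise.

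Some items are protected from the waiver:

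- the pregnancy test: "Must be performed at Visit 1 and starting from Visit 2 prior to each study drug administration in females of childbearing potential";
- colonoscopy in Flow Chart 3 (footnote 1): "or if the patient had a treatment interruption followed by a clinical relapse, it must be performed between V1 and V2";
- the diary and hematocrit of early completers, which Section 6.2.1 requires to be new.

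QuantiFERON, ECG and the detailed examination have no such protection.

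**The concern.** The waiver makes sense for a direct roll-over, whose last 1311.6 visit and Visit 1 are the same day or a few days apart. It is also given, unchanged, to patients who have been away from the trial for an unspecified time. Flow Chart 3 is, by its title, for patients who lost response or remission after completing 1311.6.

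The authors saw that a gap makes some results stale, because they require a new colonoscopy after relapse and a new diary. They did not extend this to the TB test. Section 1.1 lists tuberculosis among the adverse events of anti-TNF agents, and such an agent may have been given in the gap.

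At stake is the safety screen at re-dosing, in a trial whose primary objective is long-term safety. A smaller matter is data attribution: a value taken after months off drug can be entered as 1311.6 data.

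**Working it through.** The plan gives no figure to reproduce. The check is a comparison of texts followed by simple addition.

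**Texts side by side**

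| Item | Body text | Flow chart |
|---|---|---|
| TB assay | 2.3: obtained at Visit 1 to exclude or discontinue untreated active or latent TB; negatives re-tested yearly | Marked at Visit 1, but waivable under footnote 2; footnote 5 asks for a work-up only on suspicion |
| Full examination | 5.2.4: at screening | Marked at Visit 1, waivable |
| ECG | 5.2.7: recorded at Visit 1 | Marked at Visit 1, waivable |

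Sections 6.1 and 6.2.1 refer sites to the flow charts for procedures, and the exclusion list in 3.3.3 has no TB item. A site that follows the chart literally can therefore omit these tests.

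**Age of a carried-over result at first dose**

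Inputs: Visit 2, the first dose, is at Week 4 in Flow Charts 1 and 3 (4 × 7 = 28 days) and at Week 6 in Flow Chart 2 (6 × 7 = 42 days), each ±7 days. The gap is the time from the last 1311.6 visit (E1/E5 for Flow Chart 3) to Visit 1. The documents give no gaps, so the 13, 26 and 52 weeks below are assumptions.

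Age = gap + 28 days (Flow Charts 1 and 3) or gap + 42 days (Flow Chart 2). The upper window adds up to 7 days.

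| Gap | Flow Charts 1 and 3 | Flow Chart 2 |
|---|---|---|
| 6 days | 6 + 28 = 34 days | 6 + 42 = 48 days |
| 13 weeks (91 days) | 119 days | 133 days |
| 26 weeks (182 days) | 210 days | 224 days |
| 52 weeks (364 days) | 392 days | 406 days |

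**Interval between TB tests if Visit 1 is skipped**

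In the SAP's copies of the charts, the next QuantiFERON after Visit 1 is at Week 52 (Flow Chart 1, Visit 8) or Week 56 (Flow Chart 3, Visit 10). The interval is gap + 52 or gap + 56 weeks.

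- Flow Chart 1: 65, 78 and 104 weeks for gaps of 13, 26 and 52 weeks.
- Flow Chart 3: 69, 82 and 108 weeks.

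Section 2.3 intends yearly re-testing. The gap itself accounts for 13 to 52 weeks of these intervals.

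**With a 5-day limit**

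A carried-over result would be at most 5 + 28 + 7 = 40 days old at first dose in Flow Chart 1 and 5 + 42 + 7 = 54 days in Flow Chart 2.

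**The case against.** - **The waiver may not reach the TB test.** It applies only to items done at the end of 1311.6, and that trial's schedule is not available. This stands, and the TB conclusion is conditional on it.
- **Section 2.3 already requires the assay at Visit 1, and footnote 2 permits omission without directing it.** This also stands: the defect is a contradiction within the protocol. A reader might infer that the plan dispenses with an entry TB test, or that patients were in fact re-dosed on old results. The documents support neither.
- **Other safeguards exist.** Section 2.3 keeps out patients with current signs of infection or a history of serious infection. A targeted examination and the laboratory panel recur before dosing. These reduce the risk, but they do not replace an assay that Section 2.3 uses to find latent as well as active infection.
- **Direct roll-overs have no ceiling either.** A reader might take 40 or 54 days as their present maximum and express a gap patient's result as a multiple of it. Footnote 1 states only a preference and footnote 14 foresees longer gaps, so no such maximum exists today.
- **The gap is assumed, and its starting point is not always clear.** Section 3.1 mentions an extended follow-up phase, so the last 1311.6 visit in Flow Charts 1 and 2 might be later than E1/E5. The ages above are the assumed gap plus a constant and do not estimate what happened.
- **The QuantiFERON weeks come from counting columns in tables read from PDF.** A one-column error would typically move the interval by 8 weeks. It would not change the part due to the gap.
- **It may be too late.** Amendment 4 announces termination, and SAP Section 4.2 describes treatment in the past tense. If enrolment is closed, only a listing remains useful.

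**Conclusion.** The concern holds as a conflict between footnote 2 and the protocol's own safety text. All three charts waive Visit 1 assessments with no maximum age, while Section 3.1 lets early completers return after an unlimited gap. Provided that QuantiFERON, ECG and the detailed examination were done at the last 1311.6 visit (E1/E5 for Flow Chart 3), re-dosing is allowed on results aged the gap plus about 4 weeks, or 6 weeks in Flow Chart 2. For a gap of a few days there is no material harm; for a gap of months the result is old and the yearly TB interval is missed.

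A reader might also infer damage to the efficacy analysis. The documents do not support that: SAP Section 6.1 takes the efficacy and safety baselines from before first dosing in the feeder trial. The data effect is close to nil. It consists of late values entered in both CRFs and, at most, a descriptive Week 0 calprotectin value, for which SAP Table 4 opens the window at Day -999 and draws on feeder data.

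Confidence is medium, because neither the 1311.6 schedule nor the actual gaps can be seen. The correction is worth making because it is cheap and concerns patient safety.

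**What to change.** In Flow Charts 1 and 2, limit both halves of footnote 2 to patients whose Visit 1 is within 5 days of their last 1311.6 visit. Delete footnote 2 from Flow Chart 3. All other patients have the Visit 1 assessments done anew, including QuantiFERON, ECG and the detailed examination, with results entered in this trial's CRF only.

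If enrolment is complete, flag and list the age of any entry TB result carried over from more than 5 days before Visit 1.

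The cost is footnote wording in three charts, or one flag variable and a listing. The downside is that a few gap patients repeat routine screening tests that Sections 2.3, 5.2.4 and 5.2.7 already call for.

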IRB	Institutional Review Board
IRT	Interactive Response Tool
ISF	Investigator Site File
i.v.	intravenous
IVRS	Interactive Voice Response System
IWRS	Interactive Web-based Response System
LDH	Lactic Dehydrogenase
LDL	Low Density Lipoprotein
LT	Long term
MACE	Major Adverse Cardiovascular Events
MedDRA	Medical Dictionary for Drug Regulatory Activities
mg	milligram
mL	milliliter
MRI	Magnetic Resonance Imaging
MST	Medical Subteam
p.o.	per os (oral)
PCC	Protocol Challenge Committee
PMN	Polymorphonuclear
PRO-2	Patient reported outcome-2
PTT	Partial Thromboplastin Time
q4w	quaque 4 weeks (once in 4 week)
RBC	Red Blood Cell
RCTC	Rheumatology Common Toxicity Criteria
REP	Residual Effect Period
RSI	Reference Safety Information
SAE	Serious Adverse Event
s.c.	subcutaneous
SES-CD	Simple Endoscopic Score in Crohn's Disease
SOP	Standard Operating Procedures
SPC	Summary of Product Characteristics
TB	Tuberculosis

TCM	Trial Clinical Monitor
TDMAP	Trial Data Management and Analysis Plan
TMM	Team Member Medicine
TMW	Trial Medical Writer
TSAP	Trial Statistical Analysis Plan
ULN	Upper limit of normal
xg	times gravity
WBC	White Blood Cells

1. INTRODUCTION

1.1 MEDICAL BACKGROUND

Crohn's Disease (CD) is a chronic relapsing, remitting inflammatory disease of the gastrointestinal tract characterized by abdominal pain, fever, and bloody or mucus-containing diarrhea ([R13-2231](#)). The disease affects the gastrointestinal tract discontinuously from mouth to anus, but most commonly the ileum and colon (40%), followed by the small bowel only (30%), and the colon only (25%) ([R13-2232](#), [R13-2233](#)). It occurs in a relatively young population and there is no marked sex difference.

The annual incidence of CD seems to be increasing with more recent estimates varying from 7.9 to 20.2 cases/100,000, and a prevalence of 161 to 319 cases/100,000 in North America and Europe ([R13-2231](#)). Mucosal lesions may be complicated by perforation and fistula formation, which may require hospitalization for medical or surgical management.

Because of myriad symptoms, clinical status is measured using clinical indexes. The most widely used, in clinical trials, is the Crohn's Disease Activity Index (CDAI) ([R97-2689](#)). At the mucosal level, the extent of disease can be graded following ileocolonoscopy according to the Crohn's Disease Endoscopic Index of Severity (CDEIS).

Remission of clinical symptoms and endoscopic mucosal healing are predictors of long term improved clinical outcomes, including sustained steroid-free clinical remission, decreased need for surgical intervention, reduction in hospital admissions, improvement in quality of life, and increased work productivity ([R13-2413](#)). There is a poor correlation between CDAI and CDEIS. It has been reported that mucosal healing may be better than CDAI for the prediction of long term prognosis ([R13-2295](#), [R13-2294](#)).

The mainstay of treatment of moderate to severe CD has been with glucocorticoid therapy, azathioprine, or 6-mercaptopurine ([R13-2269](#)). More recently, biologics consisting of monoclonal antibodies directed at cytokines, thought to mediate the pathology, have been used extensively for this indication. In clinical studies of infliximab, adalimumab, and certolizumab pegol, induction of CDAI remission at 4 weeks were in the range of 25 to 35% in contrast to placebo rates of 4 to 12%. At six months, response rates were of approximately 60% and remission rates of 40-50%, compared with 20% in placebo-treated patients. Adverse events reported with these agents include drug-induced lupus, lymphoma, demyelinating diseases, and serious and opportunistic infections, including tuberculosis and systemic fungal infections. Many patients lose response to TNF inhibitors over time, in part due to development of neutralizing or depleting anti-drug antibodies (ADA). Overall, one third of patients fail to respond to initial anti-TNF

therapy (primary non-response), and another third lose their response over time (secondary non-response) ([R13-2268](#), [R13-2267](#), [P13-05746](#), [R13-2264](#), [R13-2266](#), [R13-2265](#)). Thus, there remains a significant unmet medical need for better treatments of this disease.

BI 655066/ABBV-066 (risankizumab) is a humanized antibody that is directed against IL-23 p19. Although the etiology of Crohn's Disease (CD) is unknown, data suggest that there is altered immune regulation at the epithelial barrier, leading to overproduction of inflammatory cytokines, tissue destruction, and aberrant tissue repair. Among the cytokines implicated in CD pathogenesis, data at the genetic, human biology and clinical level strongly implicate IL-23 in this disease. In a Phase II placebo-controlled trial of the IL-12/IL-23 antagonist mAb ustekinumab in Crohn's Disease, 34.1 to 39.7% of patients receiving single doses of ustekinumab (1 mg/kg, 3 mg/kg, or 6 mg/kg) had a CDAI response at 6 weeks, compared to 23.5% of patients receiving placebo ([R12-5152](#)). In a recent Phase II placebo-controlled trial of the specific IL-23p19 antagonistic mAb MEDI-2070 in moderate to severe Crohn's Disease, 46% of exclusively anti-TNF pretreated patients achieved a clinical response (vs. 25% on placebo) while 27% achieved a clinical remission (vs 15% on placebo) ([R15-1973](#)). Therefore, an IL-23 antagonist, whether directed against the p40 or p19 subunit, is likely to be an effective treatment for CD.

